8.3.6 SERIOUS ADVERSE EVENT REPORTING

The investigator must record all serious adverse events and report to DSMC and IRB according to timetable for reporting specified in section 10.1.4.

All SAEs will be reported using the FDA 3500A Mandatory MedWatch report form. SAE form can be found at:

<http://www.fda.gov/downloads/AboutFDA/ReportsManualsForms/Forms/UCM048334.pdf>

To submit an SAE, email as follows within **24 hours of becoming aware of the event:**

To: [contact]
[contact]
[contact]
[contact]

Subject: 19-2862 SAE Report Form

Attach: SAE form completed and signed by the Investigator

Follow-up of unresolved serious adverse events

Any SAEs that are unresolved at the time of the initial report submission should be followed up by the investigator for as long as medically indicated, and an updated SAE report submitted at the time new information regarding the event becomes available.

8.3.7 PRODUCT COMPLAINTS OR MEDICATION ERRORS (INCLUDING OVERDOSE)

A product complaint is a verbal, written, or electronic expression that implies dissatisfaction regarding the identity, strength, purity, quality, or stability of a drug product. Individuals who identify a potential product complaint situation should immediately contact Takeda

Pharmacovigilance or designee (see below) and report the event. Whenever possible, the associated product should be maintained in accordance with the label instructions pending further guidance from a Takeda Quality representative.

A medication error is a preventable event that involves an identifiable patient and that leads to inappropriate medication use, which may result in patient harm. While overdoses and underdoses constitute medication errors, doses missed inadvertently by a patient do not. Investigators must record all medication errors (including overdose) on the appropriate CRF form. Individuals who identify a potential medication error situation should immediately contact Takeda (see below) and report the event.

For Product Complaints or Medication Errors (Including Overdose), contact Takeda Pharmacovigilance

Phone: [name]

Email: [contact].

Product complaints in and of themselves are not AEs. If a product complaint results in an SAE, an SAE form should be completed and sent to Takeda Pharmacovigilance

8.3.8 REPORTING OF PREGNANCY

While a pregnancy test will be performed on female participants of childbearing potential as part of the screening process to ensure no pregnant patients are enrolled, all participants of childbearing potential will be counseled to utilize appropriate contraception. If a pregnancy does occur in a female patient on trial, the pregnancy will be reported as an SAE. The outcome of all pregnancies of female study subjects (spontaneous miscarriage, elective termination, normal birth or congenital abnormality) must be followed up and documented even if the participant was discontinued from the study treatment. Should pregnancy occur during a participant's trial participation, the participant will be immediately discontinued from the study treatment and followed-up per trial protocol.

If a pregnancy occurs, the following must be documented in the SAE report:

- Relevant family history
- Previous pregnancies (overall number, deliveries, spontaneous miscarriages, etc.)

- Current pregnancy (last menstrual period, expected delivery date, any amniocentesis, chorionic villus sampling, in-vitro fertilization)
- Outcome of pregnancy (i.e. full term, premature birth, spontaneous miscarriage, elective termination. If premature birth, specify gestational age in weeks. If elective abortion, specify any medical reason)
- Details of birth (i.e. DOB, weight, sex, healthy baby, sick baby, congenital anomaly/birth defect, still birth, multiple births, sickness manifestations, etc.)
- Any complications, infections, illness during pregnancy

8.3.8.1 PROCEDURES FOR REPORTING DRUG EXPOSURE DURING PREGNANCY AND BIRTH EVENTS

If a woman becomes pregnant or suspects that she is pregnant while participating in this study, she must inform the investigator immediately and permanently discontinue study drug. The sponsor-investigator must fax a completed MedWatch Form to the Takeda Pharmacovigilance or designee immediately (see Section 8.3). The pregnancy must be followed for the final pregnancy outcome (i.e., delivery, still birth, miscarriage) and Takeda Pharmacovigilance or designee will request this information from the sponsor-investigator.

If a female partner of a male patient becomes pregnant during the male patient's participation in this study, the sponsor-investigator must also immediately fax a completed Pregnancy Form to the Takeda Pharmacovigilance or designee. Every effort should be made to follow the pregnancy for the final pregnancy outcome.

Pregnancy Reporting Form:

US FDA MedWatch 3500A:

<http://www.fda.gov/Safety/MedWatch/HowToReport/DownloadForms/default.htm>

8.4 UNANTICIPATED PROBLEMS

8.4.1 DEFINITION OF UNANTICIPATED PROBLEMS (UAP)

The Office of Human Research Protection (OHRP) considers unanticipated problems involving risks to participants or others to include, in general, any incident, experience, or outcome that meets all of the following criteria:

- Unexpected in terms of nature, severity, or frequency given (a) the research procedures that are described in the protocol-related documents, such as the IRB-approved research protocol and informed consent document; and (b) the characteristics of the participant population being studied;
- Related or possibly related to participation in the research (“possibly related” means there is a reasonable possibility that the incident, experience, or outcome may have been caused by the procedures involved in the research); and
- Suggests that the research places participants or others at a greater risk of harm (including physical, psychological, economic, or social harm) than was previously known or recognized.

This study will use the OHRP definition of UAP.

8.4.2 REPORTING OF UNANTICIPATED PROBLEMS

Incidents or events that meet the OHRP criteria for UAPs require the creation and completion of a UAP report. It is the Site PI’s responsibility to report UAPs to their IRB. The Lead PI is responsible for reporting the UAP to the IRB and the UCCC DSMC. The UAP report will include the following information:

- Protocol-identifying information: protocol title and number, PI’s name, and the IRB project number;
- A detailed description of the event, incident, experience, or outcome;
- An explanation of the basis for determining that the event, incident, experience, or outcome represents a UAP;
- A description of any changes to the protocol or other corrective actions that have been taken or are proposed in response to the UAP.

9 STATISTICAL CONSIDERATIONS

9.1 STATISTICAL HYPOTHESES

- Primary Efficacy Endpoint(s):
Disease Control Rate (DCR) of brain metastases at 3 months (13-week MRI), where DCR is defined as complete response (CR), partial response (PR), or stable disease (SD) as defined by the RANO-BM criteria. The primary analysis will test the following hypotheses:

$$H_0: p \leq 0.60$$

$$H_1: p \geq 0.90$$

where p represents the proportion of patients who meet the DCR criteria.

- Secondary Efficacy Endpoint(s):
 - 1a. Time until any CNS progressive disease (PD) by RANO-BM criteria
 - 1b. Time until any local PD (ie, in brain lesions identified at the time of enrollment) by RANO-BM criteria
 - 1c. Time until any distant brain PD (ie, new brain lesions that were not present at the time of enrollment) by RANO-BM criteria
 - 1d. Time until progression at any site using RANO-BM for intracranial disease and RECIST for extracranial disease
 - 2a. Time until death from any cause
 - 2b. Time until brain metastases-specific mortality, defined as intracranial progression as a component of cause of death
 3. Cumulative rate of best responses for complete response (CR), partial response (PR), stable disease (SD), by RANO-BM criteria
 4. Time until the administration of whole brain-radiotherapy (WBRT)
 5. Quality of life will be assessed using standardized QOL metrics (EORTC QLQ C30/BN 20)
- Exploratory Endpoint(s):
 1. Quantification of corticosteroid agent and dose at screening and at each clinical assessment

9.2 SAMPLE SIZE DETERMINATION

The goal of this single arm phase 2 trial is to demonstrate specifically the short-term safety and efficacy of a strategy of brigatinib alone for patients with asymptomatic or mildly symptomatic brain metastases. Using contemporary prospective data on brigatinib (Camidge, et al. "Exploratory Analysis of Brigatinib Activity in Patients with Anaplastic Lymphoma Kinase-Positive Non-Small-Cell Lung Cancer and Brain Metastases in Two Clinical Trials" Journal of Clinical Oncology (2018): JCO-2017), our alternate hypothesis (H_1) is that brigatinib alone will result in a CNS disease control rate (DCR) of 90% at 3 months in this population. An upper 1-sided 1-sample exact binomial test with 19 analyzable patients will have 88.5% power to detect a difference between the null hypothesis (H_0) of 60% or less DCR and H_1 , assuming a type-1 error rate of 0.025. Assuming a 20% dropout rate, it is expected that 23 patients would need to be enrolled to yield 19 evaluable patients (i.e. completers).

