1. Analysis of blood at baseline and at progression to correlate blood-based markers with clinical outcomes.
2. To characterize corticosteroids administration before and after brigatinib initiation

Population:

- **Sample size**

- Maximum number of participants that can be enrolled is 35 (allow for screen failures)
- Minimum number of participants to be enrolled 19 (number of participants needed to answer scientific question/aims)

- **Gender** Male and Female
- **Age Range** 18-100 years
- **Demographic group:** Patients with brain metastases from ALK+ lung cancer without prior treatment with brigatinib
- **General health status:** ECOG ≤2
- **Geographic location:** United States

Phase:

II

Participating Sites:

University of Colorado, Mayo Rochester, City of Hope Los Angeles

Description of Study Intervention:

Brigatinib, an oral tyrosine kinase inhibitor (TKI) targeting anaplastic lymphoma kinase (ALK)

[figure not shown]
Study Duration:

4 years

Participant Duration:

2 years

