9.4.2 ANALYSIS OF THE PRIMARY EFFICACY ENDPOINT(S)

The primary efficacy endpoint is 3-month Disease Control Rate (DCR) of brain metastases (based on the 13-week MRI), where DCR is defined as complete response (CR), partial response (PR), or stable disease (SD) as defined by the RECIST 1.1 criteria and brain metastases are defined per RANO-BM criteria. A 1-sided 1-sample exact binomial test will be performed to test the null hypothesis (H_0) that $p \leq 0.60$, where p represents the proportion of patients who meet the DCR criteria. With 19 evaluable patients, the test will have 88.5% power to detect an alternative hypothesis value of $p \geq 0.90$ when the type 1 error rate is controlled at 0.025. In addition to the hypothesis test, the proportion of patients meeting the 3-month DCR definition will be summarized using the sample proportion and a 95% exact confidence interval.

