9.4.6 PLANNED INTERIM ANALYSES

This study is designed to enroll approximately 23 patients in order to yield 19 evaluable patients. Given this relatively small sample size, there are no planned interim analyses for efficacy or futility. After 19 evaluable patients have completed a 3-month brain MRI (allowing for analysis of the primary endpoint of DCR of brain metastases at 3 months), an initial analysis of the primary endpoint and short-term data on secondary endpoints may be performed.

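### Section 9.2 pairs 20% dropout with 23 enrolled to give 19 evaluable patients; at 20% the number is 24, and 23 allows only about 17% loss

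*Combined protocol and SAP*

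**What the plan says.** Section 9.2 sets the design as a one-sided exact binomial test of a 60% null disease control rate against 90%. It gives the power for a fixed evaluable number: "An upper 1-sided 1-sample exact binomial test with 19 analyzable patients will have 88.5% power", "assuming a type-1 error rate of 0.025". It then turns that number into an enrolment figure: "Assuming a 20% dropout rate, it is expected that 23 patients would need to be enrolled to yield 19 evaluable patients (i.e. completers".

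Three other places bear on the point:

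- Section 9.4.2 repeats the power on the same basis: "With 19 evaluable patients, the test will have 88.5% power".
- Section 9.4.6 repeats the enrolment figure more loosely, without a dropout rate: "This study is designed to enroll approximately 23 patients in order to yield 19 evaluable patients".
- The synopsis (section 1.1, Population) gives a maximum of 35, with room for screen failures, and a lower bound: "Minimum number of participants to be enrolled 19 (number of participants needed to answer scientific question/aims".

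Section 9.3 defines who counts for the primary endpoint: patients who enrol, start brigatinib and have the 13-week brain MRI.

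**The concern.** The sentence in section 9.2 fixes three quantities that determine one another: the dropout rate, the number enrolled and the number evaluable. Any two give the third, and the three printed values disagree.

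The meaning of dropout is not in doubt. The sentence counts patients enrolled and equates evaluable patients with completers, and section 9.3 defines the primary analysis set by completion of the 13-week MRI. The rate is therefore the share of enrolled patients who do not reach that set, and the conversion is division by one minus the rate.

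The 88.5% power holds for exactly 19 evaluable patients. An enrolment target that yields fewer than 19 on average, at the plan's own dropout rate, does not deliver the stated design in expectation.

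**Working it through.** **Inputs**

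- Evaluable patients required: 19 (sections 9.2 and 9.4.2)
- Null and alternative disease control rates: 0.60 and 0.90 (sections 9.1 and 9.2)
- Type I error: 0.025, one-sided (sections 9.2 and 9.4.2)
- Dropout rate 20% and enrolment 23 (section 9.2)

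**Step 1. Reproduce the stated power.** For X ~ Bin(19, p), the smallest critical value with size at most 0.025 is 16:

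- P(X ≥ 15 | 0.60) = 0.0696, too large
- P(X ≥ 16 | 0.60) = 0.0230, acceptable
- P(X ≥ 16 | 0.90) = 0.8850

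The plan's 88.5% is correct.

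**Step 2. Apply the stated dropout rate.**

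- Expected evaluable with 23 enrolled: 23 × (1 − 0.20) = 18.4
- Enrolment needed for 19: 19 / (1 − 0.20) = 23.75, rounded up to 24
- Check: 24 × 0.80 = 19.2
- Loss that 23 can bear while keeping 19: (23 − 19)/23 = 4/23 = 17.4%
- Loss that 24 can bear: 5/24 = 20.8%

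**Step 3. Possible origin of 23.** Inflating by 20% instead of dividing by 0.80 gives 19 × 1.20 = 22.8, which rounds up to 23. Rounding 23.75 down also gives 23. The documents do not say which was done, and neither meets the stated rate.

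**Step 4. Size of the effect.** Exact power at neighbouring evaluable numbers, with the critical value reset for each:

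| Evaluable | Critical value | Power at 0.90 |
|---|---|---|
| 17 | 15 | 76.2% |
| 18 | 16 | 73.4% |
| 19 | 16 | 88.5% |
| 20 | 17 | 86.7% |

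At 18 the critical value stays at 16, because P(X ≥ 15 | 18, 0.60) = 0.0328 exceeds 0.025; the size falls to 0.0082. The drop from 88.5% to 73.4% comes from the discreteness of the exact test and should not be read as the cost of the slip.

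A fairer measure averages over the evaluable number. Assume that accrual stops at a fixed N and that each patient drops out independently with probability 0.20. Average power is then the sum over k of P(Bin(N, 0.80) = k) × exact power at k:

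| Enrolled N | P(at least 19 evaluable) | Average power |
|---|---|---|
| 23 | 0.501 | 79.8% |
| 24 | 0.656 | 82.0% |

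The difference in average power is 82.0 − 79.8 = 2.2 points.

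**The case against.** The best defence is that 23 is a forecast and not a design parameter. Section 9.2 words it as an expectation, section 9.4.6 calls it approximate, and no hypothesis, critical value or analysis uses it. Under independent 20% dropout with 23 enrolled, the single most likely evaluable number is exactly 19, and the chance of reaching at least 19 is about one half. Moving to 24 raises that chance only to about two thirds, so the correction does not secure 19 either.

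Section 9.4.6 also ties the timing of a possible initial analysis to 19 evaluable patients having had the 3-month MRI. That suggests the evaluable count may govern accrual. If it does, the fixed-accrual power figures never arise. The contrast between 18 and 19 evaluable could mislead as well: exact power is saw-toothed, and 16 evaluable patients (78.9%) would give more power than 18.

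Most of this stands as an argument about weight, and it is why the point is minor. It does not make the sentence correct. A required minimum is rounded up, and section 9.2 ties 23 to a stated rate that it does not meet. No section states that enrolment continues until 19 patients are evaluable. The maximum of 35 is explained by screen failures; it leaves room for a 24th patient but does not repair the arithmetic.

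**Conclusion.** The concern holds, as a minor arithmetic error confined to section 9.2. The enrolment figure is one patient short at the stated dropout rate. This conclusion rests only on figures printed in the plan and on reading dropout as the share of enrolled patients who do not become evaluable, which is how sections 9.2 and 9.3 use the terms.

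Section 9.4.6 is not wrong on its own, since it states no dropout rate. Section 9.4.2 is correct as written. The loss of about 2 points in average power depends on fixed accrual and independent dropout, neither of which the plan specifies. If accrual runs until 19 patients are evaluable, there is no loss of power and only the forecast is off.

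**What to change.** In section 9.2, do one of the following:

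- state 24 enrolled at 20% dropout, showing 19/0.80; or
- keep 23 and state a tolerated non-evaluable rate of about 17% (4 of 23).

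If 24 is chosen, change the approximate figure in section 9.4.6 to match.

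Two clarifications are optional and do not correct further errors. One is a sentence saying that enrolment continues, within the maximum of 35, until 19 patients are evaluable for the primary endpoint. The other is to word the synopsis minimum of 19 as evaluable patients.

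The cost is one corrected figure, plus the matching one in section 9.4.6 if 24 is used. The test, the hypotheses, the error rate and the maximum of 35 do not change.

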9.3 POPULATION FOR ANALYSES

This is a modified intent-to-treat analysis. Patients who enroll and initiate brigatinib and undergo the 3-month (13-week) brain MRI assessment will be analyzed for the study primary endpoint. Secondary endpoints related to safety, tolerability or duration of therapy/progression will be conducted on all who start brigatinib.

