4 STUDY DESIGN

4.1 OVERALL DESIGN

This is a single arm phase-II study including patients with ALK+ NSCLC and brain metastases, who are either neurologically asymptomatic or have only mild neurologic symptoms (RTOG acute neurologic morbidity score 0-2) from their brain metastases, who are TKI naïve or have had prior exposure to crizotinib, but who are naïve to brigatinib and other ALK TKIs including alectinib, lorlatinib, and ceritinib. At screening and enrollment, patients will have a history and physical exam, CTCAE symptoms assessment, and brief QOL questionnaires.

At day 1, all patients will be started on brigatinib 90 mg daily for 7 days, before escalating to 180 mg daily thereafter as tolerated.

At day 8, patients will be seen for a scheduled clinic visit. Each clinic visit will include toxicity assessment and physical exam. Day 8 procedures have an allowable window of ± 4 days. Brief QOL questionnaires will be administered at baseline (Day 1), at 3 weeks (Day 21), and at 3 months (week 13) and subsequent visits every 3 months.

At 3 weeks (Day 21), patients will be seen for scheduled clinic visits and a scheduled surveillance brain MRI. Week 3 procedures have an allowable window of ± 4 days. Subsequently, patients will have scheduled clinic visits and surveillance brain MRIs at 3 months post enrollment (week 13) and at 3 month intervals for year 1 and 2 (ie, at week 26, 39, 52, 65, 78, 104).

Patients who develop CNS progression during the study will be offered palliative radiation for their brain metastases and their disease status will be recorded as CNS progression event.

Patients who experience disease progression per RECIST 1.1 or RANO BM may continue to be treated with brigatinib if, in the opinion of the treating investigator, they continue to experience clinical benefit. Note, this is an accepted treatment strategy per the contemporary NCCN NSCLC guidelines. In this case, patients will be removed from study treatment and will be followed for survival for up to 24 months from Day 1, but may continue to receive brigatinib per standard of care.

If patients do not experience disease progression, they will complete the study treatment at 24 months. Patients continuing to benefit from brigatinib in the opinion of the treating physician may remain on the drug after 24 months per standard of care.

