6.5 PROHIBITED THERAPY

At enrollment, additional systemic therapies for the treatment of lung cancer may not be taken concomitantly with brigatinib (eg, TKIs, immunotherapy, chemotherapy), but there will not be a

required washout period for prior systemic therapies, with the exception of systemic treatment with strong cytochrome p-450 (cyp)3a inhibitors, strong cyp3a inducers, or moderate cyp3a inducers, which are not permitted within 14 days of study enrollment (refer to current brigatinib IB version for comprehensive list).

Patients may be switched to regimens containing these therapies by the treating physician if brigatinib is discontinued due to progressive disease or brigatinib intolerance by the patient. Disease progression and the associated changes in therapy will be recorded, the patient will be removed from study treatment, and they will continue to be followed for survival (for up to 24 months from Day 1).

Use of alternative or herbal therapy while on study treatment is only allowed if no known interactions with the study medication exist and must be documented and approved by the sponsor.

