9.4 STATISTICAL ANALYSES

9.4.1 GENERAL APPROACH

Standard statistical conventions will be used, such as statistical hypotheses will be tested controlling the type 1 error rate at 0.05 for 2-sided tests and at 0.025 for 1-sided tests, and p-values less than 0.05 will be considered significant. When confidence intervals are reported 95% confidence intervals will be used. In addition to the formal statistical tests of the primary and secondary endpoints, descriptive summary statistics will be produced. All analyses will be performed by a biostatistician in the University of Colorado Cancer Center Biostatistics Core. The full analysis data set includes all patients who are enrolled onto the trial. The safety data set includes all patients who receive at least one treatment of brigatinib. SAS® software 9.4 M5 (SAS Institute Inc., Cary, NC, USA) or later will be used for the statistical analyses of the study.

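### The primary DCR test includes only starters who have the 13-week MRI, and no rule counts CNS failure before week 13, so early failures can leave the denominator and bias DCR upward

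*Combined protocol and SAP*

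**What the plan says.** Section 9.3 calls the analysis modified intent-to-treat and then states: "Patients who enroll and initiate brigatinib and undergo the 3-month (13-week) brain MRI assessment will be analyzed for the study primary endpoint". The next sentence uses a wider set for other endpoints: "Secondary endpoints related to safety, tolerability or duration of therapy/progression will be conducted on all who start brigatinib". Section 9.2 plans 23 enrolments "to yield 19 evaluable patients (i.e. completers") under the condition "Assuming a 20% dropout rate". Section 9.4.2 bases the tested DCR on the 13-week MRI.

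Two statements come close to a rule for early failures, but neither is tied to the primary test:

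- Section 4.1 says of patients with CNS progression that "their disease status will be recorded as CNS progression event".
- Section 9.4.1 defines a wider set: "The full analysis data set includes all patients who are enrolled onto the trial". It does not assign that set to the DCR test, and section 9.3 assigns a different one.

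For progressors who continue brigatinib, section 4.1 says "patients will be removed from study treatment and will be followed for survival for up to 24 months from Day 1". For those who stop it because of progression, section 6.5 says "the patient will be removed from study treatment, and they will continue to be followed for survival". The notes to the Schedule of Events (section 1.3) place the termination visit within 30 days of the last dose and survival follow-up every 6 months after that.

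**The concern.** Whether a patient enters the primary analysis depends on an event after treatment starts, and that event is related to the outcome. CNS progression can be detected at the week-3 MRI or through clinical worsening (section 8.1.1). A patient who progresses then may leave study treatment, have the termination assessments well before week 13, and never have a 13-week MRI. As section 9.3 is written, that patient is outside the primary set rather than counted as a failure.

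There is a second gap. If a patient receives salvage CNS radiation before week 13 and does have the scan, the plan does not say whether the earlier progression stands. Such a scan could be read as stable disease or response.

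The trial asks whether brigatinib alone gives acceptable CNS control in the first 3 months, so the patients in whom it fails earliest matter most to the answer. There is no control arm in which a similar bias might offset this one.

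**Working it through.** **Inputs.** From section 9.2: null DCR 0.60, alternative 0.90, one-sided exact binomial test at 0.025, 19 analysable patients, 20% dropout, 23 enrolled. I assume that all 23 start brigatinib. The share *e* of starters who fail early and lack a 13-week MRI is not in the documents, so a range is shown.

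**The plan's own figure.** The smallest cutoff with P(X ≥ r | 19, 0.60) ≤ 0.025 is r = 16. Its size is 0.0230 and its power at 0.90 is 0.885, which matches the stated 88.5%.

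**DCR among those analysed.** If all controlled patients are scanned and early failures are not, DCR among those analysed is 0.60/(1 − e). For e = 0.10 this is 0.60/0.90 = 0.667.

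**Type I error when the true DCR among starters is 0.60.** Four settings are shown:

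- A: 19 analysed, success at 16 or more.
- B: 23 starters, only early failures missing.
- C: 23 starters, 20% missing in total, with early failures inside the 20%.
- D: 23 starters, early failures missing, plus 20% uninformative dropout among the rest.

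In B to D the cutoff is recalculated for the number analysed (16/19, 17/20, 18/21, 19/22, 19/23, and likewise for smaller numbers).

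| e | Share of all failures, e/0.40 | DCR among analysed | A | B | C | D |
|---|---|---|---|---|---|---|
| 0% | 0% | 0.600 | 0.023 | 0.019 | 0.014 | 0.014 |
| 5% | 12.5% | 0.632 | 0.042 | 0.026 | 0.027 | 0.025 |
| 10% | 25% | 0.667 | 0.079 | 0.053 | 0.052 | 0.044 |
| 15% | 37.5% | 0.706 | 0.145 | 0.105 | 0.099 | 0.077 |
| 20% | 50% | 0.750 | 0.263 | 0.190 | 0.190 | 0.132 |

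In A to C, the last row treats the whole planned dropout as early CNS failure, so it is an extreme case. The 20% is a planning figure, not a strict cap. If excluded patients fail at the same rate as the others, there is no inflation: size stays at 0.023 with 19 analysed, or 0.014 with 23 starters and 20% dropout.

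**Reversal of a positive result.** This needs no assumed rate. Exact one-sided p-values against 0.60:

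| Reported | p | One failure added | Two failures added |
|---|---|---|---|
| 16/19 | 0.023 | 16/20, p=0.051 | 16/21, p=0.096 |
| 17/19 | 0.0055 | 17/20, p=0.016 | 17/21, p=0.037 |
| 18/19 | 0.0008 | 18/20, p=0.0036 | 18/21, p=0.011 |

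One omitted failure reverses 16/19, and two reverse 17/19. 18/19 survives two. At a true DCR of 0.90 with 19 analysed, the chance of 16 or 17 successes is 0.885 − 0.420 = 0.465, so these are not rare results. The plan itself allows for 23 − 19 = 4 patients not analysed.

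**The case against.** The text does not order early failures to be discarded, and several provisions reduce the risk:

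- Time to CNS progression, with rates at follow-up intervals, is planned in all starters, and week 13 is a scheduled assessment. Selective loss would therefore be visible.
- Section 8.1.1 lists the MRIs without an on-treatment condition. Section 4.4 follows patients for 2 years, including those with CNS progression. Section 5.5 regards the later MRIs as standard of care. Section 7.2 asks for every effort to obtain information on withdrawals, and it requires stopping only for progression that needs another therapy, which differs from section 4.1.
- The route is narrow. Only one MRI is scheduled between baseline and week 13, and target-lesion progression needs both a 20% increase and 5 mm growth in a lesion.
- The assumed shares are large. At e = 10%, a quarter of all failures would be both early and unscanned. At 5% with 23 starters, the size is close to nominal.

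These points stand as limits on how likely and how large the bias is. They do not remove it. A 13-week MRI after early progression is possible but not assured, and a secondary endpoint that shows the missing failures does not correct the primary p-value or confidence interval. It is also fair that the inflation depends on the dropout model, which is why setting D is shown. It gives the lowest figures and is the one comparable with the power costs given with the fix.

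**Conclusion.** The concern holds, and it should be fixed before the primary analysis. The plan states a population rule under which a patient with CNS progression or CNS radiation before week 13 and no 13-week MRI is not analysed, and no other provision brings that patient back as a failure. The bias runs in favour of the treatment. It arises only if exclusion is related to CNS failure, and its size depends on an early-failure share that the documents do not give. At 5% of starters it ranges from negligible (0.025 with 23 starters) to 0.042 with 19 analysed. At 10% the type I error is 0.044 to 0.079, and at 15% it is 0.077 to 0.145, against a nominal 0.025. Whatever the share, one omitted failure is enough to overturn a result at the success boundary.

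**What to change.** Amend sections 9.3 and 9.4.2 as follows:

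1. Define the primary set as all patients who start brigatinib and have either a 13-week MRI or documented CNS failure before it.
2. Count as not controlled any RANO-BM CNS progression, or CNS radiation for progression of brain metastases, up to the 13-week assessment. This applies whether or not a 13-week MRI exists and whatever a later scan shows.
3. Treat as non-evaluable only starters with no 13-week MRI and no evidence of CNS failure. Report their number and reasons.
4. State in advance how a death before week 13 without documented CNS progression is counted.
5. Add a sensitivity analysis in all starters with every missing 13-week MRI counted as failure. It should not be primary: with 23 starters and success at 19 or more, power at a true DCR of 0.90 falls to 0.55 with 10% missing (0.90 × 0.90 = 0.81) and 0.19 with 20% missing (0.90 × 0.80 = 0.72).

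Sections 4.1 and 7.2 should also be reconciled on which progressors leave study treatment.

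**Cost.** No visits or scans are added, because the week-3 MRI and the termination brain MRI and RANO-BM assessment are already scheduled. The reported DCR may be lower. The rule is slightly conservative, because early failures stay while some controlled patients drop out. Let *p* be the true DCR, *f* the share of failures that are early, and *d* = 0.20 the dropout among patients without early failure. The evaluable share is then (1 − p)f + (1 − d)[p + (1 − p)(1 − f)], and DCR among evaluable patients is p(1 − d) divided by that share. With f = 0.5, 0.60 becomes 0.48/0.84 = 0.571 and 0.90 becomes 0.72/0.81 = 0.889.

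Power at 0.90 under the proposed rule (f and d are assumptions):

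| f | 23 starters, cutoff recalculated | Enrol to 19 evaluable, 16/19 | Expected starters for 19 evaluable |
|---|---|---|---|
| 0 | 0.80 | 0.885 | 23.8 |
| 0.25 | 0.78 | 0.867 | 23.6 |
| 0.5 | 0.76 | 0.847 | 23.5 |
| 1 | 0.72 | 0.806 | 23.2 |

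With 23 starters and no dropout, power is 0.927. The current rule also gives 0.80 with 23 starters at f = 0. Its apparent 0.94 at f = 0.5 is the bias itself, since DCR among those analysed is then 0.90/0.95 = 0.947. Continuing enrolment to 19 evaluable patients under the new definition recovers most of the planned power for about 23 to 24 starters on average.
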